Standard At-Home Conservative Therapy: Mometasone nasal rinse, mouth taping, nasal strip, lateral positional therapy. Risk of *Mometasone* include systemic absorption of the topical glucocorticoid rinse and risk of aggravating cataract and glaucoma. Risk of the *mouth taping* and *nasal strip* include skin irritation from the adhesive. Risk of *lateral positional therapy* include shoulder and hip pain during the day after sleeping.

Benefits of both treatment interventions include a reduction or cessation of snoring, leading to an improvement of quality of life for both the participant and their sleeping partner.

The consent process informs a volunteer about the study, indicates that participation is voluntary, and that he/she has the right to stop at any time. Risks are listed in the informed consent form and described orally during the consent process.

2.g Early Withdrawal of Participants

Participants may withdraw at any point in the study. The Principal Investigator can also withdraw a participant at his discretion if he determines the participant is not using the intervention correctly, for failure to adhere to the intervention, or for undermining integrity of the study.

If a participant decides to withdraw from all components of the research study, the investigator will discontinue all the current and scheduled research activities in the study.

2.h When and How to Withdraw Participants

A participant can withdraw consent for the study at any time. Participants will be allowed to end participation in the study at any point should they desire. All participants will have an exit interview to ascertain any adverse effects and discuss the reason for ending participation. The study team will follow them for safety reasons up to 30 days after stopping use of the study intervention.

2.i Data Collection and Follow-up for Withdrawn Participants

If a participant has ended participation, the only data that will be collected are the data from the exit interview and the data collected prior to withdrawal. There will not be any other follow-up or data collected from these subjects.

Data collected up to this point will not be used in the analysis, and further data will not be collected from these participants.

D3 Study Intervention

3.a Description

3a.1 Interventional Arm

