The Mandibular Advancement Device for this study will be the ProSomnus Sleep Device. It is a sleep device intended to reduce nighttime snoring and mild to moderate Obstructive Sleep Apnea in adults by holding the lower jaw forward during sleep. This

position prevents the tongue and throat from collapsing into the airway, preventing obstruction. The amount of protrusion is determined by the device's arches or by the expansion screws within the device itself. A dentist prescribes the device at an initial visit where the amount of advancement is also determined. From there, the device can be advanced manually by the participant, either through inserting the next upper or lower arch in the series of arches, or by manually adjusting the screws in the device. This is done incrementally until the prescribed advancement is achieved. Since the device can be adjusted by the participant, only an initial visit is required for fitting.

3a.2 *Conservative treatment arm*

The conservative treatment will consist of four different interventions used simultaneously.

Mometasone nasal rinse. Mometasone is an anti-inflammatory corticosteroid used for a variety of conditions. Among respiratory tract conditions, Mometasone is used for COPD, nasal polyps, asthma, chronic sinusitis, and allergic rhinitis. A nasal sinus saline irrigation (aka “Neti-Pot”) type system will deliver the Mometasone to the participant’s sinuses. For participants randomized to the conservative treatment arm, daily use of nasal lavage with mometasone will be required. Each nasal rinse will contain 2 mg of Mometasone in a 240 ml Nasal Sinus Rinse kit. The Mometasone rinse will have minimal systemic effects, as previous studies with topical steroid rinses have shown no adverse outcomes^{26,27}.

External nasal dilatory therapy. External nasal dilatory therapy consists of a stiffened adhesive strip (a “breathe-right” strip) applied externally across the nasal alae nightly. The goal is to retract and stabilize the nasal alae, dilating the anterior nasal valve and encouraging nasal breathing.

Mouth taping. Participants will receive a package of Johnson and Johnson Band-Aid Woven Adhesive Bandages (1” x 3”) tape and instructed to apply it vertically over the upper and lower lips at the columella. This encourages the participants to breathe through their nose instead of their mouth and decrease snoring amount.

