Lateral positional therapy. Lateral positional therapy consists of interventions to encourage lateral sleeping (i.e., “snore” ball, hugging pillow), which reduces the anatomical obstructions of snoring.

3.b *Treatment Regimen*

3b.1 *Interventional arm*

After the device is fitted by the maxillofacial physician, the participant will take the device home and wear it during sleep for a period of four weeks.

3b.2 *Conservative treatment arm*

Participants in this group will undergo a nightly medicated nasal rinse consisting of 240 ml nasal saline lavage with 2mg Mometasone. This mometasone nasal rinse will occur for a 4-week period prior to beginning the other three conservative therapy interventions. After the 4-week period of the mometasone nasal rinse the other three

conservative therapy interventions (external nasal dilator, mouth taping, and lateral positional therapy) will begin and occur simultaneously each night as described above.

3.c Method for Assigning Participants to Intervention Groups

The participants will be assigned using permuted block randomization in a 1:1 allocation between two arms: the MAD intervention and the conservative therapy intervention.

3.d Preparation and Administration of Study Intervention

The MAD will be delivered to the participants during the initial visit with the maxillofacial physician. Participants will self-insert the device nightly during the trial.

For the conservative therapy arm, the participants will be supplied with a roll of Johnson and Johnson Band-Aid Woven Adhesive Bandages 1" x 3", one box of Breath-Right strips (either small, medium, or large), and one Neti-Pot. The participants will receive their topical glucocorticoid prescription through the mail from AdvancedRx, which is a compound pharmacy in Fort Washington Pennsylvania that specializes in nasal delivery of medications.

3.e Participant Compliance Monitoring

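### Section 2.h promises up to 30 days of safety follow-up after stopping, but 2.i rules out follow-up beyond the exit interview for the same people and excludes their data from analysis without exempting safety data

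*Combined protocol and SAP*

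**What the plan says.** Three adjacent sections of D2 deal with people who leave the study.

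- **2.g** covers full withdrawal. All current and scheduled research activities stop under this condition: "If a participant decides to withdraw from all components of the research study".
- **2.h** covers ending participation in general. It provides that "All participants will have an exit interview to ascertain any adverse effects and discuss the reason for ending participation", and then that "The study team will follow them for safety reasons up to 30 days after stopping use of the study intervention".
- **2.i** also covers anyone who has ended participation. It limits data to the exit interview and what was gathered before withdrawal, and adds: "There will not be any other follow-up or data collected from these subjects". On use of the data it says: "Data collected up to this point will not be used in the analysis".

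Elsewhere, D3 section 3.e plans to collect side-effect rates in the two groups, and section I promises a published discussion of adverse effects of both treatments. E7 section 7.a removes participants with serious adverse effects from the study, and 7.d collects adverse events from source documentation. F3 names a per-protocol primary analysis, describes comparisons of outcomes, and defines no safety population. F1 allows for 33% drop-out, taking 60 participants to 40 evaluable.

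**The concern.** There are two separate problems.

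The first is operational. Sections 2.h and 2.i give opposite instructions about the same people after the exit interview. A coordinator who follows 2.i withholds a safety protection that the protocol promises one section earlier.

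The second concerns reporting. People who stop because of side effects are among the most informative about tolerability. Section 2.h interviews them about adverse effects, yet 2.i gives an analyst a textual reason to set that information aside. If the exclusion were applied to the rates in 3.e and the discussion in section I, the reported tolerability of each arm would describe only those who stayed. Participants removed under 7.a may be affected too. That is an inference, because 7.a does not refer to 2.i.

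**Working it through.** **Step 1. Can 2.h and 2.i be reconciled?** Three readings were tried.

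| Possible reconciliation | Result |
|---|---|
| 2.h means clinical contact and 2.i means research data only | Fails: 2.i rules out other follow-up as well as other data |
| 2.g settles it | Fails: 2.g is limited to withdrawal from all components, whereas 2.i applies to everyone who has ended participation |
| 2.h is about people who complete the study | Fails: its exit interview asks why participation ended, so it includes early leavers |

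The conflict therefore stands for anyone who ends participation without refusing all further contact.

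**Step 2. What does the exclusion cover?** Section 2.i does not say which analysis it means. F3 is the only analysis specification and contains no harm analysis, which favours an efficacy-only meaning. But 3.e and section I foresee harm summaries, and no section says whether leavers are counted in them. The text permits both readings.

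**Step 3. How many people could be involved?** From F1, 60 × (1 − 0.33) = 40.2, or 40 evaluable, which reproduces the plan's figure. With 30 randomized and 20 evaluable per arm, about 10 per arm are lost if losses are even. This is a loss of evaluable cases. It may include losses before treatment, non-adherence and missing partner responses, so it is not a count of withdrawals after starting treatment.

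**Step 4. Which way would omission push a side-effect rate?** Let *w* be the share of an arm's treated participants who withdraw, *Rc* the side-effect rate among those retained, and *Rw* the rate among those who withdraw.

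- All-treated rate = (1 − *w*)*Rc* + *w**Rw*
- Reported rate minus all-treated rate = −*w*(*Rw* − *Rc*)

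The documents give neither *Rc* nor *Rw*. The table is an illustration only. It assumes *Rc* = 2/20 = 10%, and in the first three rows that all 10 lost had started treatment. The 10% withdrawal share in the last two rows is also an assumption.

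| *w* | *Rw* | All-treated rate | Reported 10% is |
|---|---|---|---|
| 10/30 | 0/10 | 2/30 = 6.7% | 3.3 points too high |
| 10/30 | 1/10 | 3/30 = 10.0% | correct |
| 10/30 | 5/10 | 7/30 = 23.3% | 13.3 points too low |
| 0.10 | 0 | 0.90 × 10% = 9.0% | 1.0 point too high |
| 0.10 | 0.50 | 9.0% + 5.0% = 14.0% | 4.0 points too low |

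The sign depends on whether leavers had more or fewer side effects than those who stayed. These rows are not bounds.

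**The case against.** The strongest reply is that the reporting half depends on one contested reading. An exit interview held to ascertain adverse effects has little purpose if its answers are then barred from every harm summary, so 2.i was probably meant for efficacy. Neither 3.e nor section I restricts itself to completers. This stands: the documents show an ambiguity, not a decided exclusion of safety data.

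Other channels also exist. Section 3.e provides two-weekly check-ins, 7.d collects adverse events from source documents, and 7.a, 7.e and 7.f keep investigation and reporting of serious events in place. These reduce the practical loss but do not remove the conflict. A literal bar on further data in 2.i sits badly with 7.d collection after exit, so it cannot be assumed that 7.d fills the 30 days. The consent form is not in the reviewed text and may settle contact and data use after withdrawal.

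A reader might infer more than the documents support:

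- **That 2.i forbids all follow-up.** It keeps the exit interview, and the conflict concerns what comes after.
- **That the published side-effect rates will be too low.** Step 4 shows that direction cannot be derived. Early leavers have had less exposure and could have fewer events.
- **That serious adverse event reporting stops.** Nothing in 2.i withdraws the reporting duties in E7.
- **That the arms have known, different exposure, such as eight weeks of rinse against four of the device.** Section 3b.2 states a 4-week rinse before the other measures. Continuation is an inference from 3a.2, which says "The conservative treatment will consist of four different interventions used simultaneously".

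**Conclusion.** The conflict between 2.h and 2.i is certain on the current text and should be corrected, because following 2.i removes a promised safety protection. The effect on by-arm side-effect rates is conditional. It arises only if the exclusion in 2.i is applied to safety data, and its size and direction are unknown. The loss of about one third allowed for in F1 means the affected group need not be small, but says nothing about how many leave because of harm. The primary outcome, the sample size and the planned efficacy comparison are untouched, and F3 plans no harm test that could be invalidated.

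**What to change.** Make three changes of wording.

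1. **2.i, follow-up.** State that the 30-day safety follow-up in 2.h, and adverse-event collection during it, continues after withdrawal unless the participant refuses further contact, for example by withdrawing from all components under 2.g.
2. **2.i, use of data.** Limit the exclusion to the per-protocol efficacy analysis.
3. **F3.** State that adverse-event and exit-interview data from everyone who started assigned treatment (first mometasone rinse or first night with the device) are tabulated by assigned arm, including those who withdrew or were removed under 7.a, as far as consent permits.

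The cost is the redrafting, one safety table, and a check of the consent form on use of data after withdrawal. The 30-day contacts are already promised in 2.h, so they are new work only if staff now follow 2.i.

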Informed consent will be obtained at the start of study visit prior to any research activity. To minimize the possibility of coercion or undue influence during the consent process, patients will be given the option to read through and sign the consent with the RC or alone. We will also remind the patient prior to the consent process that their ability to receive care will not be impacted by the presence or absence of consenting to the study, and that if they do consent, they can withdraw at any time. To minimize the coercion to finish the study, the participants will be reminded that if they do not finish the study, they will still be compensated on a pro-rated basis for the previously completed steps.

All assessments will be conducted either in person or virtually via HIPAA-compliant online surveys at baseline and then throughout the study course virtually or over the telephone.

2.e Randomization Method and Blinding

Participants will be randomized according to computer-generated code to receive either the mandibular advancement device or standard at-home therapy. [name] will provide the randomization table to the co-investigator, [name].

Due to the nature of the randomization process, blinding during the data collection phase will not be possible as the primary researcher will have to coordinate a specific initial visit with either the maxillofacial physician or [name], the otolaryngology specialist. Participants cannot be blinded either as the treatment modalities differ in a way which makes adequate blinding not possible. [name] will be blinded to randomization. Prior to data analysis, [name] will blind groups as “A” and “B” so that the team will not know which intervention corresponds to A and B throughout both the data analysis and manuscript writing process.

2.f Risks and Benefits

Mandibular Advancement Device. Risks of the Prosomnus sleep and snore device include drooling, temporomandibular disturbances, tooth pain, TMJ disturbances, and movements of the teeth that can change a person’s bite. All these risks are uncommon and resolve after cessation of use. These risks will be minimized using a morning

repositioning device each morning after the Mandibular Advancement Device is worn. Benefits of the device include a reduction in snoring intensity and severity.

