There will be check-ins with the study participants every two weeks conducted through the participant's preferred communication method (i.e., phone call or video call) to answer questions and ensure participants are adhering to protocol requirements. Participants will be asked to keep a paper calendar for daily notes of side/adverse effects and study barriers. The paper calendar will be mailed back to the RA after study completion, or a photo of the paper calendar will be sent attached to an email to the RA. Treatment compliance data and rates of side effects will be collected in the two groups. Collection of compliance will occur through a nightly log of compliance, which the participants will receive via REDCap from the research team and fill out throughout the study.

3.f Prior and Concomitant Therapy

Participants will not qualify for the study if they are on any concomitant therapy for snoring not assigned by the study team. Participants who have tried prior therapy for the treatment of snoring will be eligible for the study. Information will be gathered on their use of prior or current therapies when determining study eligibility.

3.g Packaging

All packing of material will consist of the consumer packaging for all interventions except for the Mometasone. AdvancedRx will ship the participants the Mometasone via UPS or FedEx delivery directly to the participant's home.

3.h Blinding of Intervention

The Principal Investigator will conduct a pre-randomization visit with all participants in which he will explain both interventions to the participants and conduct a physical

exam. The physical exam will ensure the participants are in adequate physical health to tolerate both interventions and lack nasal polyps, temporomandibular joint disorder, and structural abnormalities. After this, the Principal Investigator will leave the visit and the other members of the study team will randomize the participants. This blinds the Principal Investigator to the intervention.

Before data analysis begins, [name] will download the data and anonymize the data into “A” and “B” groups. Only [name] will know which group belongs to which. The research team will then proceed with data analysis.

3.i Receiving, Storage, Dispensing and Return

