- Events that result in such a condition where the participants may require immediate hospitalization or increase the duration of hospitalization.
- Any events that lead to a permanent or temporary physical disability in the body of the participants. Any sort of incapacity is also regarded as SAE.
- Any events that lead to any type of congenital abnormalities. It also includes any cases of birth defects resulting from the clinical trials.
- Any events where an investigator or team of investigators finds feel that it can lead to significant hazards.

7.c Classification of Events

7c.1 Relationship

An AE or SAE may or may not be causally related to the study intervention. A causal relationship means that the intervention caused (or is reasonably likely to have caused) the AE. This usually implies a relationship in time between the intervention and the AE (e.g., the AE occurred shortly after the participant received the intervention). For all AEs, it is the responsibility of the Principal Investigator who examines and evaluates the participant to determine the relatedness of the event to the study intervention.

7c.2 Severity

Severity refers to the intensity of a specific event and is a matter of individual clinical judgment.

- Grade 1: Asymptomatic or mild symptoms; clinical or diagnostic observations only; no intervention indicated
- Grade 2: Moderate; minimal, local, or noninvasive intervention indicated; limiting age-appropriate instrumental activities of daily living (ADL)
- Grade 3: Severe; or medically significant but not immediately life-threatening; hospitalization or prolongation of hospitalization indicated; disabling; limiting self-care ADL
- Grade 4: Life-threatening; urgent intervention indicated.
- Grade 5: Death related to an AE

7c.3 Expectedness

An adverse event or suspected adverse reaction is considered "unexpected" if it is not consistent with the risk information described in this protocol or on the informed consent or is not listed at the specificity or severity that has been observed; or, if an investigator

brochure is not required or available, is not consistent with the risk information described in the general investigational plan or elsewhere in the current application, as amended.

7.d Data Collection Procedures for Adverse Events

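### Section 3.h declares the PI blinded but nothing maintains that blind, and a discretionary, probably arm-aware PI withdrawal can remove a pair from the primary analysis

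*Combined protocol and SAP*

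**What the plan says.** Section 3.h describes one blinding step for the PI. He examines every participant and explains both interventions, and then: "After this, the Principal Investigator will leave the visit and the other members of the study team will randomize the participants". The section concludes: "This blinds the Principal Investigator to the intervention".

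Other sections give the PI decisions about the assigned intervention:

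- **2.g (early withdrawal):** "The Principal Investigator can also withdraw a participant at his discretion if he determines the participant is not using the intervention correctly". The grounds continue: "for failure to adhere to the intervention, or for undermining integrity of the study". No adherence threshold is given.
- **7c.1 (relationship):** for all adverse events, "it is the responsibility of the Principal Investigator who examines and evaluates the participant to determine the relatedness of the event" to the study intervention.
- **7.e (reporting):** serious adverse events go to the PI as soon as they are identified.

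On what happens to withdrawn participants, 2.i limits collection to the exit interview and what was gathered before withdrawal, and then says: "Data collected up to this point will not be used in the analysis". F3 makes a per-protocol analysis primary. It does not define the set and plans no analysis of all randomised pairs. F4 makes no adjustment for missing data.

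Sections 2.e and 3.h relabel the groups A and B just before data analysis. Section 2.e also says that "blinding during the data collection phase will not be possible as the primary researcher will have to coordinate a specific initial visit".

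**The concern.** Leaving the room conceals the assignment only while it is being made. Later the PI is asked to rule on matters that differ visibly by arm. If those rulings reveal the arm, two things follow.

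First, a report that repeats 3.h would claim an investigator blind that the trial had no means of keeping.

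Second, and more important for the estimate, the PI's withdrawal decision determines which pairs count. The partner rates the primary outcome, so the PI does not influence the rating itself. The route to bias is exclusion. A decision with no stated threshold, made after randomisation and probably with knowledge of the arm, can take a pair out of the responder comparison. If the threshold is applied more strictly in one arm, and poor adherence goes with poor response, the groups compared are no longer those that randomisation formed.

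**Working it through.** **Step 1. Can the blind survive the PI's duties?**

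- *Mechanism (3.h):* the PI's departure before allocation. No later safeguard is described: no arm-masked adherence summary, no delegated assessor, no masked review of withdrawals.
- *Relatedness (7c.1):* a duty, for every adverse event, placed on the PI who examines the participant. Section 2.f lists different risks by arm: tooth pain, jaw-joint disturbance and bite change for the device; adhesive skin irritation, steroid effects, and shoulder and hip pain for conservative therapy. Relatedness can hardly be judged without learning which applies.
- *Correct use and adherence (2.g):* a power, not a duty. Correct use of a jaw device and of a rinse, strip and tape regimen are different questions, so answering either one discloses the arm.

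The blind may hold for a pair with no adverse event and no adherence question. For the others it cannot plausibly hold.

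**Step 2. From decision to primary result.** The PI withdraws a participant (2.g). Section 2.i is headed for withdrawn participants and does not separate those withdrawn by the PI from those who chose to leave, so on its plain reading the data are dropped and the end-of-study partner CGI-I is not collected. The pair is then absent from the numerator and denominator in F3, and F4 does nothing to compensate. The A/B labels are applied after this has happened and cannot undo it.

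**Step 3. The plan's own figures (F1).** Inputs: 60 randomised, 33% drop-out, 30% control response, a rate 20% higher with the device, 20 evaluable per group.

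- Evaluable: 60 × (1 − 0.33) = 40.2, so 40.
- 95% half-width, 30% versus 50%: 1.96 × √(0.30×0.70/20 + 0.50×0.50/20) = 1.96 × √0.0230 = 29.7 points.
- If 20% higher is read as relative (36%): 1.96 × √(0.30×0.70/20 + 0.36×0.64/20) = 29.1 points.

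Both round to the stated 30%, so these figures are not in dispute.

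**Step 4. Illustration only.** The documents do not say how many withdrawals will be PI-initiated, so no expected bias can be computed. The cases below assume that every removed pair is a non-responder and that all come from one arm.

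*From 20 evaluable, 10 responders:*

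- none removed: 10/20 = 50.0%
- 1 removed: 10/19 = 52.6% (+2.6 points)
- 3 removed: 10/17 = 58.8% (+8.8 points)

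*From 30 randomised per arm, 9 responders in each (30%, no true difference), removals from the MAD arm only, difference as MAD minus conservative:*

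- 3 removed: 9/27 − 9/30 = 33.3% − 30.0% = +3.3 points
- 5 removed: 9/25 − 9/30 = 36.0% − 30.0% = +6.0 points
- 10 removed: 9/20 − 9/30 = 45.0% − 30.0% = +15.0 points

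For the second setting, the two-sided 5% pooled chi-square test was enumerated over all binomial outcomes (30 per arm, true rate 30% in both). Its type I error is 4.9% with no removals and 6.9%, 7.5% and 20.9% with up to 3, 5 and 10 non-responders removed.

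**The case against.** The strongest reply is that 3.h describes a real step and that no section says the PI is told the arm. Under 3.e the nightly logs go through REDCap and the paper calendar goes to the research assistant, so adherence information does not obviously reach the PI. A reader might infer that the stated blinding does not exist; the documents do not support that. They show a blind without protection.

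Three further inferences also go too far:

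- *That 2.e proves the PI is unblinded.* It speaks of a primary researcher, who is not identified as the PI. The same paragraph says that a person whose name has been removed is blinded to randomisation, and that could be the PI. It is a point to reconcile, not proof.
- *That the PI must judge use and adherence.* Section 2.g is permissive. Only relatedness is a duty.
- *That the PI sees the partner's daily severity ratings.* The protocol does not say who sees the replies.

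On size, the 20 per arm is already net of the 33% drop-out, so removing more pairs from it goes beyond the planned losses. That is fair, and it is why the 30-per-arm version is also shown. Responder status comes only from the end-of-treatment CGI-I, so a PI who withdraws someone mid-treatment cannot know it. That also stands, but bias does not need that knowledge: it is enough that non-adherence goes with non-response. The shifts from 20 evaluable also lie inside the 30-point margin, but that margin describes random error and does not cover a systematic shift.

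Finally, excluding non-adherent pairs would threaten the comparison even under a perfect blind. That is correct. Probable knowledge of the arm makes it worse, because an unstated threshold can then be applied differently in the two arms.

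**Conclusion.** The concern holds in a limited form. The PI blind claimed in 3.h rests on one step at allocation, has no procedure to maintain it, and cannot plausibly survive the decisions in 7c.1 and 2.g. Through 2.i and the per-protocol primary analysis, a discretionary and probably arm-aware withdrawal can remove a pair from the primary comparison, and the A/B masking comes too late to prevent this.

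The documents do not establish that the PI is in fact unblinded, that he sees outcomes, or that withdrawals would be selective. The size of any bias is therefore unknown. The rise from 50.0% to 58.8% rests entirely on assuming three removals, all non-responders and all from one arm; it is not a forecast. The exclusion rule itself is stated in the plan and does not depend on that assumption.

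**What to change.** 1. **Blinding claim.** Limit 3.h to saying that the PI completes the pre-randomisation examination before allocation and that his blinding after that is not assured. Keep the A/B masking of the analysis. Reconcile 2.e, 2.g, 3.h and 7c.1, including whether the primary researcher in 2.e is the PI.
2. **Data after a PI withdrawal.** Amend 2.i so that a PI-initiated withdrawal for use or adherence does not delete data. Where consent continues, still collect the partner CGI-I, and log the reason for withdrawal before that rating is seen. This concerns outcome data only; it does not touch the decision to stop an intervention.
3. **Analysis.** In F3, define the per-protocol set by objective adherence criteria fixed before outcomes are seen. Beside it, report the responder-rate difference in all randomised pairs with data, by assigned arm.

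The cost is a less favourable blinding statement, a little more follow-up using a survey already planned, and one additional analysis.
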